7.3. SYMPTOM RESOLUTION

Objective: To test whether HCQ or HCQ + azithromycin decreases the resolution rate for symptomatic SARS-CoV-2 infection/COVID-19 disease compared to placebo

Outcome: Symptomatic SARS-CoV-2 infection/COVID-19 disease is defined based on the following criteria:

- At least TWO of the following symptoms: Fever ($\geq 38^{\circ}\text{C}$), chills, rigors, myalgia, headache, sore throat, new olfactory and taste disorder(s), OR
- At least ONE of the following symptoms: cough, shortness of breath or difficulty breathing, OR
- Severe respiratory illness with at least 1 of the following:
 - Clinical or radiological evidence of pneumonia, OR
 - Acute respiratory distress syndrome (ARDS)

A participant will be defined as having reached the endpoint if they have two consecutive visits that do not meet the definition above. The time of the endpoint will be the midpoint between the last symptomatic day before reaching the endpoint and the first non-symptomatic day defining the endpoint. Participants who do not have the endpoint will be censored at the last time they were

known to be symptomatic. Death and hospitalization will be counted in the endpoint by assigning their follow-up to be censored at day 14.

Cohort: mITT Disease Resolution Cohort

Data sets: HCQ Disease Resolution Data Set, HCQ+A Disease Resolution Data Set

Endpoint: Resolution of COVID-19 symptoms for 2 or more days.

Stratification variables: Indicator of more than 4 days since onset of symptoms (as measured at enrollment visit)

Analysis details: Kaplan-Meier cumulative incidence curves will be estimated and plotted for each intervention including 95% confidence intervals accounting for household cluster. Curves will also be plotted by arm and stratification variable.

Cox proportional hazards models stratified by high/low risk and adjusted for baseline covariates identified above will be used to estimate the efficacy as 1 minus the hazard ratio. Due to potential clustering induced by the household design, robust standard errors will be estimated for the hazard ratio. The overall efficacy will be tested using a p-value ascertained from the Wald statistic based on the robust standard error. 95% confidence intervals will also be calculated based on the robust standard error.

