7.5. Method of Treatment Assignment

Participants will be randomized in a 1:1 ratio to placebo (ascorbic acid), or LPV/r, at the level of the household (all eligible participants in 1 household will receive the same intervention). The randomization plan will be overseen by the Study Statistician. The randomization code and resulting allocation list will be generated and overseen by the Study Statistician. The list will be blocked and stratified by site and risk level.

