The Statistical Analysis Plan will be developed and finalized before database lock and will describe the participant populations to be included in the analyses, the detailed analytical plans with endpoints and procedures for accounting for missing, unused, and spurious data. An Interim Monitoring Plan will also be developed to describe approaches for re-estimation of sample size and any planned interim analyses. This section presents a brief summary of the planned statistical analyses of the primary and secondary endpoints (these are listed in [Section 4](#)).

11.3.1. *Efficacy Analyses*

Demographic characteristics (age, sex, race) of each study group will be tabulated.

The mean age (plus range and standard deviation) by sex of the enrolled participants, as a whole and per group, will be calculated.

Primary analyses: The primary analyses will be conducted on the intend-to-treat population overall and by cohort (high-risk and low-risk). Participants randomized to each active treatment will be compared to participants randomized to placebo (ascorbic acid). If appropriate, the primary analysis will make use of all participants randomized to placebo, whether contemporaneously enrolled or not, using an Empirical Bayesian information borrowing method (described below). Due to anticipated heterogeneity in risk of disease progression, pre-specified baseline variables, including age, BMI, and days of symptoms at time of enrollment will be included in the model to increase precision.

Both primary endpoints will be analyzed using a Cox proportional hazards model with robust standard errors, adjusted for within household correlation.

As-treated analysis: The primary analyses will be repeated, replacing randomization arm by actual treatment to account for possible off-label use of and noncompliance to the investigational products.

Subgroup analyses: All subgroup analyses will be pre-specified in the Statistical Analysis Plan. Any further subgroup analyses will be considered ad hoc.

Missing Data

Due to the design of the study and retention activities, measurable outcomes are expected for all participants. However, in the unlikely event of a missing test result, the missing data will be imputed.

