1.4. RANDOMIZATION

Due to the adaptive design of the study, we implemented randomization to 12 dummy codes, stratified by site and risk cohort. Participants are randomized to 1 of 12 dummy codes that are mapped to active and control arms using an allocation ratio appropriate to the current design of the study. Participants were randomized 1:1:1 for the Hydroxychloroquine and Hydroxychloroquine + Azithromycin efficacy study.

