Hydroxychloroquine + azithromycin (HCQ+A) Efficacy Data Set This data set will include all participants in the cohort randomized to the combination hydroxychloroquine/azithromycin arm or its contemporaneous control.

Intention to Treat (ITT) Low Risk (LR) Cohort: The ITT LR Cohort includes all contacts enrolled into the study's low risk cohort (persons age 18-59 without risk factors for severe disease, including pulmonary disease, DM1 or DM2, HTN, immunocompromising condition, or BMI>30)).

Modified Intention to Treat (mITT) LRTI Cohort: The mITT LRTI cohort includes ITT HR Cohort participants who did not meet the criteria for the primary LRTI endpoint on day 1. The following data sets are created from participants in this cohort.

Hydroxychloroquine (HCQ) LRTI Efficacy Data Set This data set will include all participants in the cohort randomized to hydroxychloroquine or contemporaneous control.

Hydroxychloroquine + azithromycin (HCQ+A) LRTI Efficacy Data Set This data set will include all participants in the cohort randomized to the combination hydroxychloroquine/azithromycin arm or its contemporaneous control.

Modified Intention to Treat (mITT) Disease Resolution Cohort: This cohort includes mITT Cohort participants who meet the COVID-19 disease criteria on day 1 (Section 7.3). The following data sets are created from participants in this cohort.

Hydroxychloroquine (HCQ) Disease Resolution Data Set This data set will include all participants in the cohort randomized to hydroxychloroquine or contemporaneous control.

Hydroxychloroquine + azithromycin (HCQ+A) Disease Resolution Data Set This data set will include all participants in the cohort randomized to the combination hydroxychloroquine/azithromycin arm or its contemporaneous control.

Modified Intention to Treat (mITT) Viral Shedding Cohort: This cohort includes mITT Cohort participants who do not meet the definition for clearance of viral shedding at baseline (day 1 and day 2 negative swabs). The following data sets are created from participants in this cohort.

Hydroxychloroquine (HCQ) Viral Shedding (VS) Data Set This data set will include all participants in the cohort randomized to hydroxychloroquine or contemporaneous control.

Hydroxychloroquine + azithromycin (HCQ+A) Viral Shedding (VS) Data Set This data set will include all participants in the cohort randomized to the combination hydroxychloroquine/azithromycin arm or its contemporaneous control.

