4.1.1. LRTI objective

Objective: To test the efficacy of HCQ and HCQ + azithromycin compared to placebo to prevent progression to LRTI, among persons with SARS-CoV-2 infection who are at high risk of progression.

Outcome: LRTI, defined by resting SpO₂<93%, sustained for 2 readings 2 hours apart AND presence of subjective dyspnea or cough within the first 14 days of follow-up.

Cohorts: mITT LRTI Cohort

Data Sets: HCQ LRTI Efficacy Data Set, HCQ+A LRTI Efficacy Data Set

Definition of Endpoint: A participant will be defined as having the endpoint if they have two resting SpO₂ readings less than 93% two hours apart but not more than 48 hours apart AND report subjective dyspnea (defined as a response of “somewhat or higher” on the “trouble breathing” question on flupro) or cough (defined as “somewhat or higher” as self-reported wet or dry cough) within 24 hours of the time the SpO₂ is reported during the first fourteen days of follow-up. The event time will be recorded as the day of the first SpO₂ reading less than 93% with the presence of subjective dyspnea or cough. Participants who do not reach this endpoint will be censored at the last time that the endpoint was ascertained not to be present. Hospitalization or death due to COVID-19 may be a competing risk. Per FDA guidance, participants who are hospitalized or die due to COVID-19 will have an event time that is the first of LRTI, hospitalization or death.

Analysis Details:

Kaplan-Meier cumulative incidence curves will be estimated and plotted for each intervention including 95% confidence intervals accounting for household cluster.

Cox proportional hazards models stratified by site and adjusted for baseline covariates identified above will be used to estimate the efficacy as 1 minus the hazard ratio. Due to potential clustering induced by the household design, robust standard errors will be estimated for the hazard ratio. The overall efficacy will be tested using a p-value ascertained from the Wald statistic based on

Confidential

the robust standard error. 95% confidence intervals will also be calculated based on the robust standard error. If there are too few endpoints to fit a Cox model then the proportion of participants meeting the endpoint in the first 14 days will be reported. Each active arm will be compared to the control arm separately using Fisher's Exact test.

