4.1.3. Duration of Shedding Objective

Objective: To separately estimate and test the efficacy of HCQ and HCQ + azithromycin placebo to reduce SARS-CoV-2 viral shedding in high and low risk participants combined.

Outcome: Time to clearance of nasal SARS-CoV-2, defined as 2 consecutive negative swabs (swabs collected daily Day 1 through Day 14).

Cohort: mITT Viral Shedding Cohort

Data sets: HCQ VS Data Set, HCQ+A VS Data Set

Endpoint: The endpoint time will be set as the day of the first negative swab. Hospitalization and death are also competing risks for this outcome; however, clearance is a positive outcome whereas hospitalization and death are negative outcomes that may impede our ability to detect clearance. Participants who are hospitalized or die will have their event time censored at day 14. Other participants who do not have 2 consecutive negative tests will be censored on the day of their last positive test.

Analysis details:

Same as Section 4.1.1.

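### Randomization is stratified by site and risk level, but no pooled time-to-event model carries both factors; the cost is usually small, and a wording change fixes it.

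*SAP*

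**What the plan says.** **Allocation.** Protocol 7.5: "The list will be blocked and stratified by site and risk level". SAP 1.4 agrees: dummy codes are assigned "stratified by site and risk cohort".

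**LRTI, SAP 4.1.1.** "Cox proportional hazards models stratified by site and adjusted for baseline covariates identified above". This analysis is confined to high-risk participants (SAP 2.2: "The mITT LRTI cohort includes ITT HR Cohort participants"), so it needs no risk term.

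**Viral clearance, SAP 4.1.3.** The objective is "to reduce SARS-CoV-2 viral shedding in high and low risk participants combined", but the analysis details read only "Same as Section 4.1.1". The model is therefore stratified by site, with no risk term, in a pooled cohort.

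**Symptom resolution, SAP 7.3.** "Cox proportional hazards models stratified by high/low risk and adjusted for baseline covariates identified above". This too is a pooled cohort, now with risk and no site. The section's other stratification variable (more than 4 days of symptoms) is mentioned for plotting the curves.

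**LPV/r co-primary endpoints, protocol 11.3.1.** A Cox model with household-robust standard errors, in which "pre-specified baseline variables, including age, BMI, and days of symptoms at time of enrollment will be included in the model". Site and risk level are not named. The analyses are to be run overall and by cohort.

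**Covariates.** SAP 4.1 fixes age, sex at birth and time since symptom onset for all efficacy analyses. SAP 2.1 adds a baseline variable to the primary analyses if the arms look imbalanced at p<0.10. By contrast, the QTc model in SAP 6.1 adjusts for both site and cohort.

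**The concern.** An analysis should normally reflect the factors that restricted the randomization. When a Cox model omits a prognostic factor, its hazard ratio moves toward 1 even if the arms are perfectly balanced on that factor. When the omitted factor was also a randomization stratum, the model-based standard error ignores the balance that the design enforced. It is then too large, and the test rejects less often than its nominal level.

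The SAP gives no reason for using a different single factor in each pooled analysis. In 4.1.3 the omission looks like a side effect of the cross-reference: a model suited to a high-risk-only cohort was carried into a combined one.

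The p<0.10 rule in SAP 2.1 does not close the gap. Site is not among its variables. Risk cohort is balanced by design, and the imbalance test is itself adjusted for risk strata. Imbalance is also the wrong trigger, because the attenuation does not depend on it.

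At stake are some power and a hazard ratio shifted toward 1, not the validity of the test.

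**Working it through.** **1. Reproduce the planned size (protocol 11.1.1: HR 1.5, 80% power, two-sided 5%, 99 events and 173 participants per arm).**
- Freedman: (1.960 + 0.842)² × [(1 + 1.5)/(1.5 − 1)]² = 7.85 × 25 ≈ 196.2, so 197 events in total, or 98.5 per arm, rounded up to 99.
- With 60% events and 5% dropout (Synopsis), N per arm = 98.1/0.60/0.95 = 172.1, or 99/0.60/0.95 = 173.7. The plan's 173 is reproduced.

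**2. Large-sample attenuation from one omitted factor.** Setup: exponential times, 10-day control median, 14-day window. Power = Φ(½·√events·ln HR − 1.96). The effect of each factor is an assumption: half the participants high-risk, and six equal sites (the protocol allows up to six).

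| Model | Omitted effect (assumed) | HR | Power |
|---|---|---|---|
| 4.1.3 type: true HR 1.6, 200 events (SAP 1.5.2), risk omitted | none | 1.600 | 91.4% |
| | risk ratio 1.5 | 1.585 | 90.3% |
| | risk ratio 2 | 1.558 | 88.0% |
| | risk ratio 3 | 1.503 | 82.2% |
| 7.3 type: true HR 1.5, 198 events (2 × 99), site omitted | none | 1.500 | 81.4% |
| | site SD 0.2 | 1.489 | 79.9% |
| | site SD 0.3 | 1.475 | 78.1% |
| | site SD 0.5 | 1.438 | 72.4% |

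Worked row: ½ × √200 × ln 1.558 − 1.96 = 7.071 × 0.4434 − 1.96 = 1.175, and Φ(1.175) = 88.0%. This approximation charges nothing for stratifying more finely and takes no account of the balanced allocation. Simulation allows for both.

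**3. Simulation.** 173 per arm, true HR 1.5, balanced allocation within 6 × 2 = 12 site-by-risk cells, 5% dropout, no covariates, no household clustering, no interim looks. Entries are estimated HR / power. There were 4,000 trials per row, except 1,500 for the row marked *.

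| Risk ratio, site SD | Neither | Site only (4.1.3) | Risk only (7.3) | Both |
|---|---|---|---|---|
| 1, 0 | 1.501 / 87.5% | 1.502 / 87.0% | 1.501 / 87.7% | 1.502 / 86.7% |
| 1.5, 0.2 | 1.477 / 84.8% | 1.488 / 85.1% | 1.489 / 85.9% | 1.500 / 85.9% |
| 2, 0.3 | 1.449 / 81.0% | 1.469 / 83.5% | 1.477 / 84.4% | 1.504 / 85.8% |
| 2, 0.5* | 1.422 / 77.2% | 1.474 / 82.7% | 1.443 / 79.9% | 1.509 / 84.6% |
| 3, 0.5 | 1.382 / 71.2% | 1.420 / 77.1% | 1.432 / 78.8% | 1.499 / 85.1% |

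Change in power from one factor to both:
- No heterogeneity: −0.3 (from site only) and −1.0 (from risk only).
- Mild (1.5, 0.2): +0.8 and 0.0.
- Moderate (2, 0.3): +2.3 and +1.4.
- Site SD 0.5 with risk ratio 2: +1.9 and +4.7 in this run; separate runs at site SD 0.5 gave about 3 to 5.
- Both effects extreme (3, 0.5): +8.0 and +6.3.

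**4. Type I error (null simulations).** With both strata it is 4.8% to 5.2%. In the (3, 0.5) case it falls to 2.5% with neither factor, 3.4% with site only and 4.0% with risk only. The error is on the conservative side.

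**5. With age in every model.** 600 trials, risk ratio 2, site SD 0.3, half of high-risk status due to age, Monte Carlo error about 1.5 points. Neither: 1.442 / 79.8%. Site only: 1.458 / 82.2%. Risk only: 1.461 / 83.0%. Both: 1.480 / 82.8%. The hazard ratio still moves, but the power difference between one factor and both is within simulation error.

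**6. A much smaller trial.** Assumed: 70 per arm, six unequal sites, true HR 1.8, 1,500 trials. With no heterogeneity, power was 84.0% with risk only and 80.4% with full site-by-risk strata. At (1.5, 0.2) it was 80.5% against 79.4%, and at (2, 0.3) 79.5% against 78.7%. A separate run put the largest loss at about 3 points.

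**The case against.** The strongest reply has four parts.

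- **The SAP models already carry one factor each.** The right contrast is one factor against both, which is 1 or 2 points at moderate heterogeneity. A reader might take the 77% to 81% power of the neither-factor column (risk ratio 2) as the loss in this trial. That column describes no Cox model in the SAP. This part stands.
- **Planned covariates overlap with risk.** Age and BMI help define the high-risk cohort, so adjusting for them recovers part of what a risk stratum would give. This stands in part: diabetes, hypertension, lung disease and immunosuppression also define the cohort, and site is not recovered at all.
- **Protocol 11.3.1 is silent rather than exclusive.** It calls itself a brief summary, its covariate list is open, and it defers detail to an SAP. A reader might infer that the LPV/r analyses exclude both factors, or that all of them are diluted by risk. The documents do not support either inference: by-cohort analyses are planned, and the Synopsis has the virologic endpoint analyzed separately in each risk population. The SAP supplied covers only the first three arms, so LPV/r handling is unspecified rather than wrong. This part stands, which is why the point is limited to the overall analyses.
- **Site effects are speculative, and fine strata can cost power.** No document says that outcomes differ by site, and with small cells the cure can be worse than the omission. This stands, and it shapes the fix.

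The hazard ratio is also non-collapsible, so part of the shift is a difference between a marginal and a conditional quantity rather than bias in the ordinary sense.

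**Conclusion.** The mismatch is certain from the text: both factors restrict the randomization, and no pooled time-to-event model is specified with both. The direction is also settled, toward a hazard ratio nearer 1 and a somewhat conservative test. A reader might infer that the tests are invalid or that false positives increase; the null simulations show the opposite.

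The size is an assumption, because the documents quantify neither site nor risk effects. At 173 per arm without covariates, moving from one factor to both is worth about -1 to +2 points of power for none-to-moderate heterogeneity. It is worth about 3 to 5 points if site effects are strong (log-hazard SD about 0.5). Larger gains appear only when a threefold risk ratio is assumed as well, and nothing in the documents supports that. Planned adjustment for age and BMI should reduce the part due to risk.

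These figures use the LPV/r design. The HCQ analyses quoted from the SAP belong to a comparison stopped early for operational futility, and its enrolment is not in the documents, so the gain there could be nil. This is a consistency correction that is worth making because it is cheap, not a threat to the conclusions.

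**What to change.** - **SAP 4.1.3:** replace the bare cross-reference with its own model statement, adding risk cohort as a stratum alongside site.
- **SAP 7.3:** add site alongside risk cohort, and list the covariates instead of pointing back to them.
- **Protocol 11.3.1 (and any LPV/r SAP):** state that the overall Cox models for both co-primary endpoints account for site and risk level, and that by-cohort analyses account for site.
- **Throughout:** keep the household-robust standard errors and the planned covariates.
- **Sparse cells:** state before unblinded analysis how small sites are pooled, or stratify by one factor and enter the other as a covariate when site-by-risk cells are thin.

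The cost is wording only, since both variables are recorded at randomization. The statistical downside is up to about 1 point of power at 173 per arm if neither factor is prognostic. With full site-by-risk cells in a much smaller trial (assumed 70 per arm) it is up to about 3 points; the sparse-cell rule is there to limit that loss.

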1.5.1. LRTI and Hospitalization Endpoints

Overall sample size will depend on the number of events observed. To detect at least 50% treatment efficacy in reducing LRTI or hospitalization/death under a null hypothesis of no reduction, four interim monitoring analyses with stopping for futility and efficacy based on the O'Brien-Fleming bounds and 90% power, the trial is designed to achieve 93 events per pairwise comparison for the LRTI and hospitalization endpoints. For two active arms and one control arm, the total number of events required for each endpoint is 124.

As the initial sample size target, 165 per arm was chosen for each experimental group (HCQ, HCQ + azithromycin), assuming a control arm rate of approximately 30% and 5% dropout rate.

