1.5.2. Viral Shedding Endpoint

Assuming the median time to cessation of viral shedding is 10 days, with a constant baseline hazard for cessation of shedding, 90% statistical power, 1-sided type I error rate of 2.5% for efficacy and early stopping for futility, the design (including interim analyses) can detect 60% or greater increase in the rate of shedding cessation in the combined high- and low-risk cohorts with 200 viral clearance events per pairwise comparison.

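### SAP 7.3, and 4.1.3 by cross-reference, define efficacy as 1 minus HR for favourable events, so the SAP's own clearance target would be reported as -60% efficacy

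*SAP*

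**What the plan says.** SAP 4.1.1 (LRTI) specifies Cox models "stratified by site and adjusted for baseline covariates identified above will be used to estimate the efficacy as 1 minus the hazard ratio". The matching design target in SAP 1.5.1 is "To detect at least 50% treatment efficacy in reducing LRTI or hospitalization/death", so there the event is unfavourable and the formula fits.

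SAP 7.3 uses the same formula for symptom resolution, with the stratification changed: the models are stratified by "high/low risk and adjusted for baseline covariates identified above will be used to estimate the efficacy as 1 minus the hazard ratio". The event being modelled is given as "Endpoint: Resolution of COVID-19 symptoms for 2 or more days". The objective above it reads "To test whether HCQ or HCQ + azithromycin decreases the resolution rate for symptomatic SARS-CoV-2 infection/COVID-19 disease".

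SAP 4.1.3 (duration of shedding) writes no formula of its own. Its analysis details are "Same as Section 4.1.1". The same section says that "clearance is a positive outcome whereas hospitalization and death are negative outcomes", and SAP 1.5.2 says the design "can detect 60% or greater increase in the rate of shedding cessation".

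Neither document reverses the scale for the favourable endpoints. The change history in SAP section 10 records only a title-page correction.

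**The concern.** When the event is bad, an effective drug lowers its hazard: HR is below 1 and 1 minus HR is positive. When the event is recovery or clearance, an effective drug raises the hazard: HR is above 1 and 1 minus HR is negative. Sections 7.3 and 4.1.3 therefore define an efficacy measure that falls as the drug works better.

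The verb in the 7.3 objective adds to the confusion. Read literally, it makes a slower recovery the aim. The same verb stands in SAP Table 1 beside endpoints counted as proportions of days with fever, symptoms or low saturation, where a decrease is a benefit. Section 7.3 analyses time to resolution, where a decrease in the rate is a harm.

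At stake is the direction of the reported percentage and its confidence interval for one primary endpoint (viral clearance) and one secondary endpoint (symptom resolution). A percentage labelled efficacy can be quoted in an abstract or a pooled table without the curves that would show the true direction.

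**Working it through.** **Inputs**
- Clearance target: 60% increase in cessation rate, 200 events per pairwise comparison, 90% power, one-sided 2.5% (SAP 1.5.2). The SAP does not write a hazard ratio here; HR = 1 + 0.60 = 1.6, active/control, follows from the stated increase.
- Four interim analyses and one final (SAP 1.5). O'Brien-Fleming bounds are named only for LRTI (SAP 1.5.1) and are assumed here for clearance.
- 1:1:1 allocation, so 1:1 in each comparison (SAP 1.4).
- LRTI target: 50% efficacy (SAP 1.5.1), that is HR 0.5 active/control.

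**Step 1: reproduce the 200 events**
- Schoenfeld, fixed design: 4 × (1.960 + 1.282)² / (ln 1.6)² = 191 after rounding up. A simulated inflation of 1.027 for a five-look O'Brien-Fleming efficacy bound gives about 196.
- Freedman: ((1.6 + 1)/(1.6 − 1))² × (1.960 + 1.282)² = 198.
- With O'Brien-Fleming-type futility bounds as well (simulated inflation about 1.09): about 207.

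The stated 200 lies among these values, so HR 1.6 is the effect the design assumes.

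**Step 2: apply the SAP formula at the target**

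1 − 1.6 = −0.60, that is -60% efficacy. On the scale of SAP 1.5.2, 1.6 − 1 = +60%.

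**Step 3: confidence interval at 200 events (no clustering or covariates)**
- SE(log HR) = 2/√200 = 0.1414.
- HR: 1.6 × exp(±1.96 × 0.1414) = 1.21 to 2.11.
- 1 − HR: -60% (-111% to -21%). HR − 1: +60% (+21% to +111%).
- z = ln(1.6)/0.1414 = 3.32, two-sided p = 0.0009.

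If household clustering inflated the variance by 1.3 (assumed range 1.0 to 1.3), SE = 0.1414 × √1.3 = 0.161. The interval on the 1 − HR scale becomes -119% to -17%, still wholly below zero.

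**Step 4: the mirror-image harm**

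HR = 1/1.6 = 0.625 (0.47 to 0.82) would be reported as +37.5% efficacy (+18% to +53%), with the same |z| and p-value.

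More generally, the significance limits at 200 events are exp(±1.96 × 0.1414) = 1.32 and 0.76. Any significant benefit would be reported as -32% or lower, and any significant harm as +24% or higher.

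**Step 5: does reversing the hazard ratio rescue the formula?**

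| Orientation | LRTI target, 1 − HR | Clearance target, 1 − HR |
|---|---|---|
| active/control | 1 − 0.5 = +50% | 1 − 1.6 = -60% |
| control/active | 1 − 2.0 = -100% | 1 − 0.625 = +37.5% |

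No single orientation gives both targets a positive sign, and 4.1.3 imports the LRTI text whole. Even with the sign right, +37.5% does not match the 60% in SAP 1.5.2.

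**Step 6: symptom resolution**

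The SAP gives no effect target for this endpoint. The protocol's table in 11.1.1, which belongs to the later lopinavir-ritonavir stage, labels the hazard ratio active/control and uses 1.5 as the design value. On the 7.3 formula that would be 1 − 1.5 = -50%.

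**The case against.** The strongest reply is that this is only a label. The hazard ratio, a two-sided Wald p-value and the event count are the same either way, the Kaplan-Meier curves show the direction, and any analyst would notice a sign at odds with them. No interim decision depended on it either: SAP section 5 says enrolment stopped for operational futility and no interim analyses were done. All of that stands, and it limits the weight of the point. It does not make the text right. An analyst who silently corrected the sign would depart from the SAP without a record and would have to choose between HR − 1 (+60%) and 1 − 1/HR (+37.5%), which the SAP does not settle.

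Other parts of the reply also stand:
- The figures above are for clearance, while the formula is written out for resolution. The argument about reversing the hazard ratio binds 4.1.3, which imports 4.1.1; for 7.3, active/control is the natural reading but is not stated.
- The 200 events are the design figure. The documents do not say they were reached, so the intervals are illustrative.
- Table 1 already used the verb *decreases* for a resolution rate, so the wording was awkward before SAP 1.3 changed the endpoint.

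It could also be said that the cross-reference in 4.1.3 means the model only. The text sets no such limit, and 7.3 contains the error in its own words.

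**Conclusion.** The point holds. As written, SAP 7.3 and, by cross-reference, SAP 4.1.3 report benefit as negative efficacy and harm as positive efficacy. The clearance design target would appear as -60%, and an equally strong harm as +37.5%. The sign follows from the formula and the direction of the event; it does not depend on the number of events or on the assumed variance inflation. The values rest on reading the 60% increase as HR 1.6, active/control, and the intervals on 200 events at 1:1.

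This is an error of sign and label, not of model fit or power. It should be corrected because it touches the named effect measure of a primary and a secondary endpoint.

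**What to change.** 1. In SAP 4.1.3, replace the cross-reference with its own analysis text, and amend 7.3 to match. Report HR (active/control) with values above 1 favouring active, or HR minus 1 as the percent increase in rate. Name one scale only. Keep 1 minus HR for LRTI in 4.1.1.
2. In the 7.3 objective, change *decreases* to *increases*.
3. Record both in SAP section 10 as a labelling correction.

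These cost wording and table labels only: no new data, and no change to the fitted hazard ratio, the test or the number of events.

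A separate, minor matter is stratification. SAP 1.4 stratifies randomisation by site and risk cohort, but 4.1.3 inherits site only and the 7.3 Cox model names risk only (7.3 also lists a symptom-duration indicator, used for the curves, whose role in the Cox model is unstated). Stratifying both models by site and risk, with small sites pooled, would match the randomisation. It would change the estimates slightly, so if results already exist it belongs in a sensitivity analysis.
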